8.2 Adverse Event Reporting

We do not anticipate hazardous situations for the subjects as a result of this protocol. However, standard of care procedures will be in place for verification of correct radiopharmaceutical dose and route of administration. The study Principal Investigator (PI) or his designee will report all serious adverse events (per 21CFR§312.32) to the Stanford CCTO Safety Coordinator within 10 working days of becoming aware of the event (5 days if the event is life-threatening or resulted in death) using the Adverse Events Communication Form. If the principal investigator determines the unanticipated adverse effect presents an unreasonable risk to subjects, the study will be terminated as soon as possible, but no later than 5 working days after the PI makes the determination and no later than 15 working days after first receiving notification of the effect.

9. REGULATORY CONSIDERATIONS

9.1 Institutional Review of Protocol

The protocol, the proposed informed consent and all forms of participant information related to the study (eg, advertisements used to recruit participants) will be reviewed and approved by the Stanford IRB. Any changes made to the protocol will be submitted as a modification and will be approved by the IRB prior to implementation. The Protocol Director will disseminate the protocol amendment information to all participating investigators.

9.2 Data Management Plan

The CRFs will be stored in a locked office in the Nuclear Medicine clinic. Records will be kept using OnCore.

During the clinical investigation, the Protocol Director will evaluate the progress of the trial, including periodic assessments of data quality and timeliness, participant recruitment, accrual and retention, participant risk versus benefit, performance of trial sites, and other factors that can affect study

outcome. Monitoring of the trial will occur every 8 weeks and a record of monitoring activities will be maintained by the study team.

The Stanford Cancer Institute Data and Safety Monitoring Committee (DSMC) will audit study related activities to determine whether the study has been conducted in accordance with the protocol, local standard operating procedures, FDA regulations, and Good Clinical Practice (GCP). This may include review of regulatory binders, case report forms, eligibility checklists, and source documents. In addition, the DSMC will regularly review serious adverse events and protocol deviations associated with the research to ensure the protection of human subjects. Results of DSMC audits will be communicated to the IRB and the appropriate regulatory authorities at the time of continuing review, or in an expedited fashion, as needed.

10. Statistical Considerations and Evaluation of Results

10.1 Study Endpoints

Primary endpoint:

- Number of the 20 participants with assessable pre- and post-treatment uptake (on either type) in response to HIFU local therapy.

"Assessable uptake" on a scan is defined as being successfully able to:

1. Appreciate the presence/absence of localized uptake (a "lesion"), and
2. Produce an SUV_{max} measurement for that ROI.

The rationale is that if both pre- and post-treatment uptake are assessable, then (presumably) changes in (1) and (2) have the potential to be used to evaluate treatment response in future trials. A patient may be assessable on the ^{68}Ga -PSMA-11 scan but not the ^{68}Ga -RM2-11 scan, and vice-versa.

Thus we will tabulate findings as below:

Patient #	SCAN TYPE			
	^{68}Ga -PSMA-11		^{68}Ga -RM2-11	
	--- Pre-TX --	--- Post-Tx ---	--- Pre-TX --	-- Post-Tx ---
1				
2				
3				
.				
.				
20				

The number of patients assessable on either (or both) types of scan is the primary endpoint; if at least 10 of the 20 patients are assessable on at least one type of scan, then the study will be deemed a success.

Secondary endpoint:

- None

Exploratory endpoints:

- Pre- and post-treatment $^{68}\text{Ga-PSMA-11}$ SUV_{max} and pre-post change in SUV_{max} after HIFU local therapy
- Pre- and post-treatment $^{68}\text{Ga-RM2}$ SUV_{max} and pre-post change in SUV_{max} - after HIFU local therapy

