1. OBJECTIVE

Specific Aim

To determine the feasibility of ^{68}Ga -PSMA-11 PET/MRI and ^{68}Ga -RM2 PET/MRI for evaluation of high-intensity focused ultrasound (HIFU) local therapy in patients with known prostate cancer.

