5. Approximately 45 to 60 minutes after the radiopharmaceutical IV administration, data acquisition will begin in the pelvic region and move toward the head. First, localizer MRI scans will be performed to define the table positions. After correct positioning of the spatial acquisition windows is ensured, the combined PET/MRI acquisition will be initiated with 3 to 5 table positions at a 2 to 4 minute acquisition time per table position. Only MR sequences required for attenuation correction of PET data will be acquired.
6. Vital signs (heart rate, blood pressure) will be recorded again at the completion of the study.
7. Participants will be contacted at 24 to 72 hours following the scan in order to capture potential occurring Adverse Events.

The above will be repeated approximately 6 months after HIFU local treatment, prior to standard of care biopsy to evaluate for residual disease in the prostate.

Objectives of the Study

Primary Objective

- To determine feasibility of ^{68}Ga -PSMA-11 PET/MRI and ^{68}Ga -RM2 PET/MRI for evaluation of HIFU local therapy in patients with known prostate cancer.

Secondary Objective

- None

Exploratory Objectives

- Comparison of ^{68}Ga -PSMA-11 post-treatment uptake and pre-post change in uptake in response to HIFU local therapy
- Comparison of ^{68}Ga -RM2 post-treatment uptake and pre-post change in uptake in response to HIFU local therapy

Endpoints

Primary Endpoints

- Number of participants with assessable pre- and post-treatment uptake in response to HIFU local therapy

Secondary Endpoint

- None

Exploratory Endpoints

- Pre- and post-treatment ^{68}Ga -PSMA-11 SUV_{\max} and pre-post change in SUV_{\max} after HIFU local therapy
- Pre- and post-treatment ^{68}Ga -RM2 SUV_{\max} and pre-post change in SUV_{\max} after HIFU local therapy

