5.3 Image interpretation

The PET/MRI scans will be interpreted by ABNM certified Nuclear Medicine physicians and an ABR certified Radiologists. Drs [name], [name], [name], and [name] have significant clinical experience and will be blinded to the participants' medical history and the results of other imaging modalities. Consensus read will be obtained for each scan. Each lesion will be tabulated and a comparison of lesion detection by each tracer will be conducted.

The study team will communicate the results of the scans to the referring (treating) physicians. Additional imaging/biopsy may be performed as a result of the research scan data.

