10.4 Analyses Plans

This is a pilot study that will not have pre-defined analyses plans, other than the described assessment for the number of participants for which a PET--based therapeutic response to HIFU successfully obtained. We will compare the changes in SUV_{max} after HIFU local therapy with results of biopsy done as standard of care at 6 months post-treatment, as well as with PSA values done every 3 months afterwards (ie, a decrease in uptake is expected to predict response, while stable or increased uptake is expected to indicate no response to HIFU local therapy). Data from 2 arms ($^{68}\text{Ga-PSMA11}$ done first or $^{68}\text{Ga-RM2}$ done first) will be aggregated. In the case that the treatment has worked to extent that the primary tumor is no longer visible, the disappearance will be detectable because of the correspondence between pre and post ROIs. In that case, we will consider the tumor assessable, and record the SUV_{max} as the ROI background.

There is no analysis beyond noting whether the total number of assessable patients meets or exceeds the threshold for success (10 of 20).

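### The aim is feasibility of PSMA-11 and RM2 PET/MRI, but the only success rule pools the tracers patient by patient, so success says nothing about either tracer alone

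*Combined protocol and SAP*

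**What the plan says.** Section 1 gives one specific aim: "To determine the feasibility of ^{68}Ga -PSMA-11 PET/MRI and ^{68}Ga -RM2 PET/MRI" in men having HIFU. Section 2.5 repeats it as the primary objective, and the synopsis does the same. There are no secondary objectives or endpoints.

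Section 10.1 defines the primary endpoint: "The number of patients assessable on either (or both) types of scan is the primary endpoint". The success rule follows: "if at least 10 of the 20 patients are assessable on at least one type of scan, then the study will be deemed a success". The same section recognises that the tracers can disagree within a patient: "A patient may be assessable on the ^{68}Ga -PSMA-11 scan but not the ^{68}Ga -RM2-11 scan, and vice-versa". It also provides a blank table with one row per patient and a pre- and a post-treatment column for each tracer. No count or criterion per tracer is attached to that table.

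Section 10.4 describes the evaluation: "There is no analysis beyond noting whether the total number of assessable patients meets or exceeds the threshold for success (10 of 20"). The registry outcome in 10.3 splits the count of participants by randomised scan order, not by tracer.

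**The concern.** The aim joins two tracers with *and*; the rule joins them with *or*. The study has one pre-specified conclusion, success or not, and a reader who knows the aim will take success to mean that both methods are feasible for judging HIFU response. The rule cannot carry that meaning.

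This matters because 10.1 justifies the endpoint by its use in later trials. A later trial that uses one of these tracers needs to know in how many patients that tracer gave an assessable result both before and after treatment. The pooled count does not say.

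**Working it through.** **Inputs.** Sample size 20 and threshold 10 (10.1, 10.4). The unit is the patient, counted once if assessable on either tracer (10.1). The documents state no null rate, target rate, alpha or power, so the mark of 10 cannot be reproduced; it is taken as given. No patient-level assessability rate is given either, so the check uses counting alone.

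**Set-up.** Split the 20 patients into a (assessable on PSMA-11 only), b (RM2 only), c (both) and d (neither), with a + b + c + d = 20.

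- Pooled count: U = a + b + c. The rule is U ≥ 10.
- PSMA-11 count: P = a + c.
- RM2 count: R = b + c.

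**What U guarantees.** Since P + R = U + c ≥ U, the larger of P and R is at least U/2, rounded up. That bound is reached when c = 0 and a and b are as equal as possible. The smaller of P and R can be 0 for any U up to 20 (take b = c = 0).

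| Pooled count U | Least possible count, better tracer | Least possible count, other tracer |
|---|---|---|
| 10 | 5 | 0 |
| 11–12 | 6 | 0 |
| 13–14 | 7 | 0 |
| 15–16 | 8 | 0 |
| 17–18 | 9 | 0 |
| 19–20 | 10 | 0 |

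**Examples that the rule calls a success**, with exact (Clopper-Pearson) 95% intervals:

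1. a = 10, b = 0, c = 0, d = 10. U = 10, P = 10, R = 0. For 0/20 the upper limit is 1 − 0.025^(1/20) = 0.168, so the interval is 0 to 16.8%.
2. a = 5, b = 5, c = 0, d = 10. U = 10, P = R = 5. Each tracer is at 5/20 = 25%, interval 8.7% to 49.1%, which lies wholly below one half.
3. a = 9, b = 9, c = 0, d = 2. U = 18, P = R = 9. Each tracer is at 9/20 = 45%, still short of 10.
4. a = b = 0, c = 10, d = 10. U = 10, P = R = 10.

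Examples 1, 2 and 4 have the same pooled count and the same verdict, yet the tracer counts are 10 and 0, 5 and 5, and 10 and 10. The interval for 10/20, 27.2% to 72.8%, describes the pooled rate only. For every U from 10 to 18, both tracers can fall below 10. Only 19 or 20 guarantees that one of them reaches 10, and even 20 guarantees nothing for the other.

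**The case against.** The best defence is that the rule is deliberate and openly described. Section 10.1 foresees disagreement between tracers and chooses the pooled count anyway. The background in 2.1 says that PSMA agents miss some recurrences, so the two tracers may be meant as a complementary pair, and the wording of 10.3, with no split by tracer, fits that. This reading is possible. But no section says that only the pair is meant, and if it is, the objective should say so.

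Second, tracer-level information will exist. The 10.1 table allows the counts to be read off, SUVmax is an exploratory endpoint for each tracer, and 5.3 promises that "Each lesion will be tabulated and a comparison of lesion detection by each tracer will be conducted". All of this stands, and a failing tracer would be visible. But SUVmax and lesion detection are not the feasibility count, and nothing tracer-specific bears on the verdict. The closing sentence of 10.4 should not be read too literally, since the same section plans to compare SUVmax changes with biopsy and PSA. Read as covering the primary decision only, it still leaves each tracer without a planned count or conclusion.

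Third, the examples are extremes. Section 2.1 reports that 5–10% of primary lesions are PSMA-negative and that the RM2 target is increased in 45–100% of prostate cancers, and 10.4 counts a tumour that disappears after HIFU as assessable. The first two figures are not assessability rates, but they make a very low PSMA-11 count look remote. A reader might infer from the examples that a misleading success is likely. The documents do not support that: they give no assessability rate from which to compute a probability.

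**Conclusion.** The point holds as a mismatch between the sole aim and the sole decision rule. Success establishes that at least 10 of 20 patients were assessable on one tracer or the other, and no more. It is compatible with 0/20 on one tracer, or with 5/20 on each. This rests on the wording of the rule and on counting, with no assumed rates.

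Two stronger readings should be avoided:

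- A reader might infer that success at least shows one tracer to be assessable in enough patients. It does not, because the rule works patient by patient; examples 2 and 3 meet it with neither tracer at 10.
- A reader might infer that each tracer ought to have been held to 10 of 20. The documents do not derive that mark even for the pooled count, so they give no basis for insisting on it per tracer.

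The data to be collected are not in question. What should be fixed is the conclusion that may be drawn from them. In a 20-patient pilot this is worth correcting because the correction is cheap and changes what the study can claim.

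**What to change.** - **Sections 10.1 and 10.4, with 10.3 for consistency:** keep the either-tracer count as primary if wished. Beside it, report for each tracer the number of the 20 patients assessable both pre- and post-treatment, with its exact 95% CI. State that any conclusion about a tracer's feasibility rests on that tracer's own count.
- **Success statement, and the objective in the synopsis, section 1 and section 2.5:** limit both to the patient-level form, for example: *at least half of patients were assessable on at least one of the two tracers*. Shorter wording, such as saying that one of the tracers is assessable, would bring back a tracer-level claim that the rule does not support.
- **Per-tracer threshold:** optional. If one is set, 10 of 20 or otherwise, give its reason.

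The definition of an assessable scan and the handling of disappearance after HIFU stay as they are.

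**Cost.** No extra scans, patients or data, since the table in 10.1 already holds what is needed. It takes one protocol modification with IRB approval under 9.1. The sponsor must also accept that the study may meet its pooled rule while one tracer, or both, cannot be called feasible.

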10.2 Accrual estimates

We anticipate enrolling 20 patients in total. We expect 1 to 2 patients to have residual tumor after HIFU.

10.3 Study Outcomes (ClinicalTrials.gov)

Primary Outcome

Title: Successful PET-based of Assessment of Local Therapeutic Response

Description: Therapeutic response to high-intensity focused ultrasound (HIFU) will be assessed by $^{68}\text{Ga-PSMA11}$ and $^{68}\text{Ga-RM2}$ PET scans. The outcome is the number of participants without dispersion, by randomization schedule, for which an assessment of PET--based therapeutic response to HIFU is successfully obtained.

Timeframe: 12 months

Safety outcome: No

Secondary Outcome

None.

10.4 Analyses Plans

This is a pilot study that will not have pre-defined analyses plans, other than the described assessment for the number of participants for which a PET--based therapeutic response to HIFU successfully obtained. We will compare the changes in SUV_{max} after HIFU local therapy with results of biopsy done as standard of care at 6 months post-treatment, as well as with PSA values done every 3 months afterwards (ie, a decrease in uptake is expected to predict response, while stable or increased uptake is expected to indicate no response to HIFU local therapy). Data from 2 arms ($^{68}\text{Ga-PSMA11}$ done first or $^{68}\text{Ga-RM2}$ done first) will be aggregated. In the case that the treatment has worked to extent that the primary tumor is no longer visible, the disappearance will be detectable because of the correspondence between pre and post ROIs. In that case, we will consider the tumor assessable, and record the SUV_{max} as the ROI background.

There is no analysis beyond noting whether the total number of assessable patients meets or exceeds the threshold for success (10 of 20).

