- Men deciding between whole-gland treatment (surgery or radiation) and partial-gland focal ablation. Finding a single tumor on MRI prompts consideration of focal ablation. Finding multiple and/or bilateral tumors prompts consideration of whole-gland treatment (surgery or radiation). Finding extracapsular disease (T3 / T4) prompts workup for potential metastatic cancer.

It should be noted that mpMRI has limitations: ~20% of all index lesions are missed (14), the size of high grade cancers is underestimated (15), and ~40% of men with a normal MRI have PCa on biopsy (16).

Positron emission tomography (PET) and PCa. PET tracers, such as ^{18}F - or ^{11}C -labeled choline and [^{11}C]-acetate, are used mainly for the diagnosis of recurrent (17-19) or metastatic (20) PCa. Their feasibility in primary diagnosis is limited because of uptake in benign tissue such as benign prostatic hyperplasia or inflammatory lymph nodes (21, 22). Although choline based PET/CT is widely used outside the US for imaging PCa, there have been numerous studies reporting a low sensitivity and specificity, especially at low PSA levels (23, 24). Consequently, improved molecular imaging of PCa is necessary. One novel method is PET imaging with ^{18}F -FACBC, a synthetic amino acid. Recent evaluations by Nanni et al. indicate that this tracer might be superior when compared to choline PET/CT (25). However, recent work indicates that ^{18}F -FACBC uptake in PCa is similar to that in BPH nodules (26). Prostate-specific membrane antigen (PSMA) is a transmembrane protein that elicits high interest. This cell surface protein is significantly overexpressed in PCa cells when compared to other PSMA-expressing tissues such as kidney, proximal small intestine or salivary glands. PSMA is highly overexpressed on almost all PCa (27-29). Only 5-10% of primary PCa lesions have been shown to be PSMA-negative (30, 31), making this class of radiopharmaceuticals suitable for diagnosis of primary PCa and for initial staging (32-37). Non-invasive tumor grading has also been reported (38). Recently methods have been developed to label PSMA ligands with ^{68}Ga enabling their use for PET imaging and therapy (39). Initial experience with PET/CT using Glu-NH-CO-NH-Lys-(Ahx)-[^{68}Ga (HBED-CC)] (^{68}Ga -PSMA-11) suggests that it can detect PCa relapses and metastases with high contrast by binding to the extracellular domain of PSMA, followed by internalization (40). Better localization of cancer within

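### Section 10.4 limits the feasibility result to a pass or fail at 10 of 20, with no statement of precision and no result for each tracer, and conflicts with other analyses the plan promises

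*Combined protocol and SAP*

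**What the plan says.** Section 10.1 makes the primary endpoint a count: "The number of patients assessable on either (or both) types of scan is the primary endpoint". The decision rule follows: "if at least 10 of the 20 patients are assessable on at least one type of scan, then the study will be deemed a success". A scan is assessable when readers can judge whether a lesion is present and can obtain an SUVmax for it. Section 10.2 sets the denominator: "We anticipate enrolling 20 patients in total".

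Section 10.4 opens with "This is a pilot study that will not have pre-defined analyses plans", excepting only the count of patients with a PET-based response assessment. It then adds a further analysis: "We will compare the changes in SUV_{max} after HIFU local therapy with results of biopsy done as standard of care", and also with PSA. A lesion that disappears after HIFU counts as assessable, with the background value recorded as its SUVmax. The section closes with "There is no analysis beyond noting whether the total number of assessable patients meets or exceeds the threshold for success".

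Section 10.3 registers the outcome as a number of participants with no measure of dispersion. The only breakdown it names is by randomization schedule, which is scan order and not tracer. No interval, reference rate, target rate, error rate or reason for choosing 10 appears anywhere.

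**The concern.** The closing sentence of 10.4 is a stated rule, so it cannot be put down to brevity. Taken literally, it cancels the SUVmax comparisons promised a few lines above it and the exploratory endpoints in 10.1. Taken as a remark on the primary endpoint only, it still confines the feasibility result to one word.

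Section 10.1 says why feasibility matters: if uptake is assessable before and after treatment, changes in it might be used to judge response in future trials. Designing such a trial needs an assessable rate and its uncertainty, for the tracer to be used. The objective names both tracers, but a patient counts if either one is assessable. PSMA-11 could therefore carry the study to success while RM2 did poorly, and no planned result would say so, although 10.1 already lays out the data by tracer.

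**Working it through.** **Nothing to reproduce.** The plan gives no inputs from which 20 or 10 could be derived, so the check is on how the stated rule behaves.

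**Inputs.** n = 20 and threshold 10 (10.1, 10.2). PSMA-negative share of primary lesions, from 2.1: "Only 5-10% of primary PCa lesions have been shown to be PSMA-negative". GRPr increased in 45-100% of prostate cancers (2.1). Loss of paired scans, d, is not stated and is varied here as an assumption.

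**1. Chance of passing at true assessable rate p.** P(X ≥ 10) = Σ C(20,x) pˣ(1−p)²⁰⁻ˣ, summed over x = 10 to 20.

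| True rate p | P(pass) |
|---|---|
| 0.30 | 0.048 |
| 0.40 | 0.245 |
| 0.50 | 0.588 |
| 0.60 | 0.872 |
| 0.70 | 0.983 |
| 0.80 | 0.9994 |
| 0.90 | >0.9999 |

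**2. Precision of the count.** Exact (Clopper-Pearson) limits are the 2.5% quantile of Beta(x, 21−x) and the 97.5% quantile of Beta(x+1, 20−x). For x = 20 the upper limit is 100%.

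| Count | Proportion | Exact 95% CI |
|---|---|---|
| 10/20 | 50% | 27.2% to 72.8% |
| 15/20 | 75% | 50.9% to 91.3% |
| 18/20 | 90% | 68.3% to 98.8% |
| 20/20 | 100% | 83.2% to 100% |

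All four counts receive the same label under the rule.

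**3. Chance of passing on the protocol's background figure.** Assume that PSMA-positive means assessable, so p = 0.90 to 0.95. Patients without a usable pre/post pair stay in the denominator, so the effective rate is p(1−d).

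| Loss d (assumed) | Effective rate | P(pass) |
|---|---|---|
| 0% | 0.90 to 0.95 | >0.9999 |
| 10% | 0.81 to 0.855 | 0.9997 to 0.99997 |
| 20% | 0.72 to 0.76 | 0.990 to 0.997 |
| 30% | 0.63 to 0.665 | 0.922 to 0.961 |
| 40% | 0.54 to 0.57 | 0.721 to 0.805 |
| 50% | 0.45 to 0.475 | 0.409 to 0.498 |

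The 1 to 2 residual tumors expected in 10.2 do not limit the count, because a vanished lesion is assessable under 10.4.

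**4. What the either-tracer rule hides.** If RM2 were assessable in 45% of patients (lower end of the GRPr range, used as a proxy), RM2 alone would reach 10 of 20 with probability 0.409. Combined with PSMA-11 at 0.90 and assuming independence, the either-tracer rate is 1 − 0.10 × 0.55 = 0.945, and with no loss of paired scans a pass is virtually certain. The protocol does not apply its rule to one tracer. The comparison only shows that a pass says little about RM2.

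**The case against.** The strongest reply is that this is an openly declared pilot and little is lost. The endpoint is the count, so x/20 is available and any reader can attach an interval. The closing sentence names the 10-of-20 threshold, so it most naturally concerns the primary endpoint. Section 10.1 plans SUVmax summaries for each tracer, and Section 5.3 plans a comparison of lesion detection between tracers. Much of this stands. A reader might infer that the plan allows no analysis at all or yields no estimate, and the documents do not support that. What is missing is the interval, a feasibility result per tracer, and wording that agrees with the rest of the plan.

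A reader might also infer that the rule cannot tell a method that works in a quarter of patients from one that works in three quarters. It can: it passes 1.4% of the time at 25% and 99.6% at 75%. The wide interval of 27% to 73% belongs to an observed count of exactly 10. At a true rate of 90% that count has probability of about 0.000006, and the expected count is 18.

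Nor would a confidence interval for mean SUVmax change be a clear gain. Vanished lesions take the background value and only 1 to 2 residual tumors are expected, so such an interval would partly reflect that substitution.

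**Conclusion.** The point holds as a reporting and consistency defect in 10.4. The closing sentence contradicts promised analyses or, on the kinder reading, leaves the primary result without a statement of precision and without a feasibility result for either tracer. The rule is lenient around one half, passing 59% of the time at a true rate of 50% and 24% at 40%. These figures need only n = 20, the threshold of 10 and independent patients.

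A reader might go further and infer that success is settled in advance. The documents do not support that. The 5-10% figure describes lesions lacking PSMA, not patients lacking assessable paired scans, and no attrition rate is given. With that figure as a proxy, a pass is at least 99% likely up to about 20% loss, but falls to 72-81% at 40% loss and 41-50% at 50%. The leniency is a reason to print the rule's behavior, not evidence that the outcome is known. No formal test, larger sample or new threshold is needed.

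**What to change.** Keep 10 of 20 as the success criterion. Replace the closing sentence of 10.4 with text such as:

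> The number and proportion of the 20 enrolled patients who are assessable will be reported with an exact (Clopper-Pearson) 95% confidence interval, for either tracer and for each tracer separately. Patients without a paired post-HIFU scan count as not assessable. SUVmax values and their comparison with biopsy and PSA are exploratory and descriptive, and lesions recorded as ROI background will be identified.

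Beside the threshold in 10.1, give a short reason for choosing 10 and state the rule's pass probabilities: about 5%, 59%, 98% and over 99.9% at true rates of 30%, 50%, 70% and 90%.

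The cost is a few sentences and trivial computation, using data that the 10.1 table already collects. The downside is that a success will appear with a wide interval.
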